8.2.1.1 Missing values

Missing or partial dates for TEAEs are imputed as follows for the purpose of the treatment-emergent definition:

- AE start day missing: If the month and year is on or after the time and date of the first study drug intake month and year, and before or during the month and year of EOT + 180 days, consider the AE as treatment-emergent and impute the first day of the month, and if it is earlier than the first study drug intake, impute the first study drug intake date.
- AE start day and month missing: If the year is the same year as the year of first study drug intake or later, and if the year is prior to or in the same year as the year of EOT + 180 days, consider the AE as treatment-emergent and impute the date of first study drug intake.
- If the AE start date is completely missing then the AE is considered to be treatment-emergent (for TP1, but not for TP2).

If the time of an AE occurring on the day of first study drug intake is not recorded, the AE is considered to be treatment-emergent.

The same rule applies for AEs on the day of re-initiation.

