2.3 Study periods

2.3.1 Screening period

The screening period starts with the signing of the informed consent form and ends on the day of Randomization, before the first study drug intake. This period can last up to 60 days.

During this period, the subject's SLE background medication should be maintained stable except for OCS which should be tapered to the minimum required dose and maintained stable for at least 15 days prior to Randomization [see protocol section 5.2.2.1, [D-22.031](#)].

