6.8.6.1.5 Data imputation

The purpose of imputing therapy dates is only to determine if a therapy is study-concomitant and/or study-concomitant at baseline.

Incomplete therapy end dates will be imputed with the latest date possible, e.g., if the day is missing, the last day of the respective month will be imputed, or if day and month are missing, the last day of the respective year will be imputed. End dates that are completely missing will not be imputed and the therapy is considered as ongoing.

If a therapy start date is completely missing, the earliest of study treatment start date or (imputed) therapy end date will be imputed.

Partial therapy start dates will be imputed as follows:

- Therapy start day missing: if the (imputed) therapy end date is on or after study treatment start date (or missing) and the partial therapy start date is in the same month and year as the study treatment start date, the study treatment start date is used. Otherwise, the first day of the month is used.
- Therapy start day and month missing: if the (imputed) therapy end date is on or after study treatment start date (or missing) and the partial therapy start date is in the same year as the study treatment start date, the study treatment start date is used. Otherwise, the first day of the year is used.

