8.2.1 Variables

AEs are classified as ‘Treatment-emergent AEs’ if the start date of the AE is on or after the date of first study drug intake (by time and date) up to EOT + 180 days (inclusive).

AEs with onset during TP1 are defined in the interval:

[First study drug intake (by time and date); Month 6 visit or EOT
(if EOT date is on or before Month 6 visit date)]

AEs with onset during TP2 are defined in the interval:

[Month 6 visit + 1 day; EOT].

Any AE prior to start of treatment (by time and date) in TP1 and AEs 121 days or more after EOT are considered non-treatment-emergent AEs.

TEAEs on Day 1 are reported up to 24 hours after first study drug intake in TP1 and on or after the time of first study drug intake.

TEAEs on the day of re-initiation are defined in the same way, but for the day of the re-initiation.

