- (4) Echocardiography will be performed at Visit 1 (Screening) preferably within 30 days prior to Randomization for all subjects and at Visit 8 (Month 6) in approximately 175 subjects, as part of the ancillary study. In the event of premature study treatment discontinuation during TP1 (i.e., before Visit 8), echocardiography will be performed at pEOT visit and will not be required at Visit 8.
- (5) A chest X-ray that has been performed within 6 months prior to Screening can be used (in this case, there is no need to repeat the chest X-ray at Screening).
- (6) At each pre-dose assessment, SBP/DBP measurements will be performed twice in the supine position.
- (7) On Day 1 and at Re-initiation visit, SBP/DBP assessment and 12-lead ECG will be done pre-dose and hourly until 6 h post-dose; after 6 h, subjects may be discharged if they meet the discharge criteria, otherwise SBP/DBP assessments and 12-lead ECG will be performed hourly until discharge criteria are met. If discharge criteria are not met after 12 h, the subject must be permanently discontinued. At all other visits, only pre-dose SBP/DBP assessments and 12-lead ECG will be performed.

- (8) On Day 1 and at Re-initiation visit, 24-hour ECG Holter should start before dosing. The subject must return to the site on Day 2 (Visit 2a) / Re-initiation (Visit I2) for removal of the device after 24-hour recording.
- (9) On Day 1 and at Re-initiation visit, PK samples will be collected 6 hours after dosing. At Visits 3, 4, 5, and 8, PK samples will be collected pre-dose. At pEOT visit, in the event of premature treatment discontinuation during TP1 (i.e., before Visit 8) and at EOS visit, PK samples will be collected at any time during the visit and will not be required at Visit 8.
- (10) Hematology assessments, including coagulation tests will be performed at each visit until EOS, except FU2, FU3 and FU3a, and FU3b visits.
- (11) Serum pregnancy tests will be performed at Screening and EOS. Urine pregnancy tests will be performed at all other visits. To ensure compliance, the study personnel must remind WOCBP at each visit to use the methods of contraception defined for this study from the Screening visit until 6 months after taking the last dose of study treatment.
- (12) All AEs and SAEs occurring after signing the ICF and up to 6 months after study treatment discontinuation must be reported.

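### The rules for missing AE start dates (SAP 8.2.1.1) ignore the AE end date, so some AEs recorded as over before first dose are classed as treatment-emergent

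*SAP*

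**What the plan says.** SAP 8.2.1 defines treatment-emergence by onset: an AE qualifies "if the start date of the AE is on or after the date of first study drug intake (by time and date"), up to 180 days after EOT. The same section makes the following non-treatment-emergent: "Any AE prior to start of treatment (by time and date) in TP1".

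SAP 8.2.1.1 then gives three rules for incomplete start dates:

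1. **Day missing.** If the recorded month lies between the first-intake month and the month reached 180 days after EOT, the programmer is told to "consider the AE as treatment-emergent and impute the first day of the month, and if it is earlier than the first study drug intake", replace it by the first-intake date.
2. **Day and month missing.** If the recorded year lies between the first-intake year and the year of EOT + 180 days, "consider the AE as treatment-emergent and impute the date of first study drug intake".
3. **Wholly missing.** "If the AE start date is completely missing then the AE is considered to be treatment-emergent (for TP1, but not for TP2"). No onset date is imputed.

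None of the three mentions the AE end date, and nothing else in SAP 8.2 adds such a check.

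AEs from before dosing are in the data. Footnote 12 of the schedule in SAP 12.1 states: "All AEs and SAEs occurring after signing the ICF and up to 6 months after study treatment discontinuation must be reported". On the length of screening, SAP 2.3.1 says: "This period can last up to 60 days".

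For therapies, SAP 6.8.6.1.5 does use the end date. A partial start in the first-dose month or year is moved to the treatment start date only "if the (imputed) therapy end date is on or after study treatment start date (or missing").

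**The concern.** An AE that ended before first intake must have started before first intake. A recorded end date therefore settles the question even when the start date is incomplete. The three rules discard that information and can classify as treatment-emergent an AE that 8.2.1 says is not.

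At stake is the accuracy of the safety tables. AEs shown by the sponsor's own data to precede study drug would be counted in the TEAE and TP1-onset tables. Where a date is imputed, the derived onset would be later than the resolution date, which is an impossible record.

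**Working it through.** The documents state no figure on this point, so there is none to reproduce. The check applies the three rules to example AEs, with and without an end-date condition.

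**Inputs.** The rules are from SAP 8.2.1.1. First dose on 23 May 2020 and EOT on 18 May 2021 are assumed for illustration. The added condition is: if the AE end date is before first intake, the AE is not treatment-emergent.

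| Recorded start | Recorded end | Result under 8.2.1.1 | Onset after end? | With the condition |
|---|---|---|---|---|
| May 2020, day missing | 10 May 2020 | TEAE, onset 23 May | Yes, by 23 − 10 = 13 days | Not TEAE |
| 2020 only | 10 Apr 2020 | TEAE, onset 23 May | Yes, by 20 + 23 = 43 days | Not TEAE |
| Wholly missing | 10 Apr 2020 | TEAE for TP1, no date imputed | No | Not TEAE |
| April 2020, day missing | 10 May 2020 | Not TEAE | No | Not TEAE |
| May 2020, day missing | 30 May 2020 | TEAE, onset 23 May | No | Unchanged |
| May 2020, day missing | Ongoing | TEAE, onset 23 May | No | Unchanged |

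The first three rows are wrong as the plan stands. The fourth shows that rule 1 works when the recorded month precedes the first-dose month. The last two show that the condition leaves alone the AEs whose timing really is uncertain.

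**How much of screening is exposed.** Assume first-dose dates spread evenly over a 366-day year, and count the screening days that fall in the same month (rule 1) or the same year (rule 2) as first dose.

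- Rule 1, 60-day screening. A month of n days contributes n(n − 1)/2 same-month days: 7 × 465 + 4 × 435 + 406 = 5,401. The share is 5,401 / (366 × 60) = 24.6%.
- Rule 1, 30-day screening: 5,401 / (366 × 30) = 49.2%. For 15-day screening the share is 73.8%.
- Rule 2, 60-day screening. The days lost to the previous year are 60 + 59 + … + 1 = 1,830, so the share is 1 − 1,830 / 21,960 = 91.7%. For 30 and 15 days it is 95.8% and 97.8%.
- Rule 3 applies to every screening day.

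**Number of AEs, on assumed rates only.** Take 325 subjects (SAP 2.1), 0.5 screening AEs per subject, 2% to 5% with an incomplete start date, and half resolved before dosing. None of these rates is in the documents; only the 325 is.

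- If every incomplete start were exposed: 325 × 0.5 × (0.02 to 0.05) × 0.5 = 1.6 to 4.1 AEs.
- If all incomplete starts lacked only the day, rule 1's same-month limit applies. The result is × 0.246 = 0.4 to 1.0 AEs with 60-day screening, or × 0.492 = 0.8 to 2.0 with 30-day screening.

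An arm has 325 / 5 = 65 subjects, so one misplaced subject is 1/65 = 1.5 percentage points in that arm.

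**The case against.** The strongest defence is that counting an AE of unknown timing as treatment-emergent is a common conservative choice: it over-counts rather than hides events, treats all arms alike and touches no efficacy endpoint. That stands for AEs whose timing is unknown. It does not cover an AE whose recorded end date proves that it was over before dosing.

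It can also be argued that 8.2.1 governs such an AE and that 8.2.1.1 only fills in dates for AEs already regarded as treatment-emergent. But rules 1 to 3 themselves direct the classification, on the start date alone, and a programmer following them would produce the results above.

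The therapy rule in 6.8.6.1.5 decides concomitance rather than emergence, so it is an analogy only. The argument does not depend on it.

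Several stronger readings are tempting but unsupported:

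- *Any AE that resolved in screening becomes a TEAE.* It does not. The start date must be incomplete, and under rules 1 and 2 the recorded month or year must be that of first dose.
- *A wholly missing start also produces an onset after the end.* Rule 3 imputes no date, so only the classification is wrong.
- *These AEs enter the Day 1 table.* This is possible but inferred. The imputation is stated to serve the treatment-emergent definition, and the provision on unrecorded times speaks of AEs that occur on the first-dose day. The SAP does not say whether an imputed date feeds that table.
- *The dose-placebo contrasts are diluted.* SAP 8.2.2 plans numbers and percentages by group, with no between-arm AE test. If a fraction c of subjects in every arm gained a false TEAE, independently of their other AEs, a difference p1 − p0 would become (1 − c)(p1 − p0). At the upper assumed rate, c = 0.5 × 0.05 × 0.5 = 0.0125, so 98.75% of the difference remains. Ratios move slightly towards 1.

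**Conclusion.** The rules are wrong as written in three defined cases: a day-missing start in the first-dose month, a year-only start in the first-dose year, and a wholly missing start, each with a recorded end date before first intake. The first two also give an onset later than the AE's end.

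The conclusion about the rules follows from the SAP text alone. The size does not: the documents give no count of incomplete AE dates, and zero to a few AEs across the five arms is a judgement based on the assumed rates. The consequence is limited to false entries in the descriptive TEAE and TP1-onset tables, and in the Day 1 table only if imputed dates are used there. This is a small correction to the safety derivations and has no bearing on the efficacy analyses.

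**What to change.** Add one sentence that applies to all three rules in SAP 8.2.1.1: an AE is not treatment-emergent if its end date is before first study drug intake, where a partial end date is taken at its latest possible value as in 6.8.6.1.5. Add that an imputed onset may not be later than the AE end date. Once the first condition is in place, the second serves mainly as a check on inconsistent records.

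AEs that are ongoing, that have no end date, or that end on or after first dose keep the current conservative rule. It would help to state as well whether imputed dates feed the Day 1 table. SAP 8.6.2.3 borrows the AE imputation for missing ECG dates and times, so the new wording should be read against that section.

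The cost is one or two SAP sentences and one condition in the AE derivation, using data already collected.

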7.4.5.1 Variables

The time to first severe flare during TP1, from baseline to Month 6 visit (in days) is defined as:

[Date of first severe flare – Date of treatment start date + 1] in days.

The start date of the first severe flare must be within TP1. Missing dates are imputed as follows:

- Day missing: Impute first day of the month or if earlier than first study drug intake, impute day of first study drug intake.
- Day and month missing: If the year is in the interval of (First study drug intake; Month 6) impute the first study drug intake date, otherwise keep as missing.
- If the date is completely missing, then include severe flare in the analysis and set the date to the first study drug intake date.

For subjects without any severe flares, the time to the first severe flare is censored at the Month 6 visit date or at the time of last available observation without any severe flares in TP1 if the subject discontinues study prior to Month 6.

Subjects with a severe flare during TP1 are considered as having an event ('1'), censored subjects as having no event ('0').

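### Adverse events dated only by a year after the first-dose year are given the first-dose date, and so fall into Treatment Period 1

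*SAP*

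**What the plan says.** **Adverse events (SAP 8.2.1.1).** The section opens with its purpose: "Missing or partial dates for TEAEs are imputed as follows for the purpose of the treatment-emergent definition". With day and month missing, the rule sets two conditions. The first is: "If the year is the same year as the year of first study drug intake or later". The second caps the recorded year at the calendar year in which EOT + 180 days falls. If both hold, the instruction is to "consider the AE as treatment-emergent and impute the date of first study drug intake". The next bullet covers dates with nothing recorded: "If the AE start date is completely missing then the AE is considered to be treatment-emergent (for TP1, but not for TP2".

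**Period assignment (SAP 8.2.1).** "AEs with onset during TP1 are defined in the interval" from first intake to the Month 6 visit, or to EOT if that is not later. TP2 runs from the day after the Month 6 visit to EOT. Both are set by onset date. The section gives no separate rule for partial dates.

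**Flares (SAP 7.4.5.1).** With day and month missing, and the year between first intake and Month 6, the rule is to "impute the first study drug intake date, otherwise keep as missing".

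**Therapies (SAP 6.8.6.1.5).** The treatment start date is used for a year-only start date only if the recorded year is the treatment-start year and the therapy had not ended before treatment began. "Otherwise, the first day of the year is used".

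**The concern.** For a year-only AE in a year after the first-dose year, the plan discards the one part of the date that is known. The onset moves back to the day of first intake, and 8.2.1 then reads it as a TP1 event. It may also enter the table of treatment-emergent events on the day of first intake. If the true onset was in TP2, the event is also lost from the TP2 tables.

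The period matters most for the 4 mg arm. Under SAP 2.1 its subjects still on treatment at Month 6 are re-randomized to placebo or 2 mg. An AE that began in TP2 or follow-up would then be tabulated in TP1 under 4 mg.

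For flares, a backdated event gets a time of 1 day in the time-to-event analysis although the record shows that it came later.

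**Working it through.** The plan has no figure to reproduce. The check applies the date rules literally.

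**Inputs from the documents**
- Months count as 30 days for windows (SAP 5.6), so Month 6 is Day 180 and Month 12 is Day 360 (Table 4).
- The treatment-emergent period ends at EOT + 180 days (8.2.1). With full treatment that is Day 360 + 180 = 540.

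**Assumptions, not in the documents:** full 12-month treatment, first doses spread evenly over a calendar year, and onsets spread evenly over Days 1 to 540.

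**Step 1: two example subjects**

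| | Subject A | Subject B |
|---|---|---|
| First dose | 1 Mar 2020 | 15 Oct 2020 |
| Month 6 | 27 Aug 2020 | 12 Apr 2021 |
| EOT | 23 Feb 2021 | 9 Oct 2021 |
| EOT + 180 days | 22 Aug 2021 | 7 Apr 2022 |
| AE dated 2021: possible days | 307–540 (never TP1) | 79–443 |
| AE dated 2022: possible days | year not accepted | 444–540 (after EOT) |
| AE date imputed, every accepted year | 1 Mar 2020 | 15 Oct 2020 |
| Flare dated 2021 | stays missing | 15 Oct 2020, time = 1 day |
| Flare dated 2022 | stays missing | stays missing |

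**Step 2: how much of the calendar is exposed**
- Let r be the days from first dose to year-end, uniform on 0 to 365, with mean 182.5. The share of the span in a later calendar year is (540 − 182.5)/540 = 0.66.
- The share in a year that starts on or after Day 180, where TP1 onset is impossible, has two parts. For r from 180 to 365, integrating (540 − r) gives 49,487.5. For r from 0 to 175, integrating (175 − r) gives 15,312.5. Dividing by 365 × 540 = 197,100 gives 0.25 + 0.08 = 0.33.

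**Step 3: all 365 first-dose dates, every onset day from 1 to 540**
- Every TP2 or post-EOT onset with a year-only date (100%) is imputed to Day 1 of TP1.
- For 186 of 365 first-dose dates (51%), Month 6 falls in the first-dose year, so a later-year AE cannot belong to TP1 at all.
- The flare rule accepts a later year for the other 179 (49%). Over all first-dose dates, about 25% of TP1 days lie in the following year. A year-only flare on one of those days is dated before its recorded year began.

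**Step 4: the later of first intake and 1 January of the recorded year**
- Subject A: AE 2021 becomes 1 January 2021, Day 307, TP2.
- Subject B: AE 2021 becomes Day 79 (TP1), and AE 2022 becomes Day 444 (after EOT, in neither period). Flare 2021 gets a time of 79 days instead of 1.
- About 25% of true TP2 onsets with a year-only date stay in TP2, against 0% now. For the rest, the imputed date still falls on or before Month 6.
- An accepted year is never later than the year of EOT + 180 days, so its 1 January never falls after EOT + 180 days. Treatment-emergent status is kept under the 180-day definition.

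**Step 5: interaction with 8.2.1.** That section sets the treatment-emergent limit at EOT + 180 days, then classes events from 121 days after EOT as non-treatment-emergent. With EOT on 15 August 2020, 1 January 2021 is 16 + 30 + 31 + 30 + 31 + 1 = 139 days after EOT. One sentence includes that date and the other excludes it.

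**The case against.** The strongest reply is the stated purpose: the imputation serves the treatment-emergent definition, and there it does no harm. Any accepted later year is already after first dose, so yes/no status does not depend on the backdating. That stands. It does not clear the period tables. SAP 8.2.1 assigns periods by onset date and offers no other date for these events. The bullet on completely missing dates itself chooses TP1 over TP2, so the section does drive period assignment.

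Other points stand in part:
- AEs are collected at every monthly visit and every monthly follow-up visit or call (Appendix 12.1), so the month should usually be known. The day-missing rule then keeps the recorded month. Year-only dates are probably few.
- The therapy rule serves only to classify concomitant use. It shows that the SAP respects a later recorded year elsewhere, but it is not a rule for period assignment.
- Flare data come from an external vendor (7.4.4.1), and time to flare lies outside the Type I error strategy (7.1, 7.1.1).

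Three stronger readings are tempting and not supported:
- A reader might infer that the flare rule shares the AE fault for any later year. It does not: years after the Month 6 year stay missing, as for Subject A.
- A reader might take 66% and 33% as shares of misplaced AEs. They are shares of a calendar span and apply only to year-only dates.
- A reader might infer a bias in the 4 mg versus placebo comparison. The rule is the same in every arm, and nothing in the documents shows a difference between arms.

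**Conclusion.** The concern holds with limits. Followed as written, 8.2.1.1 dates a later-year AE before its recorded year, and 8.2.1 then puts it in TP1 even where TP1 onset is impossible. Treatment-emergent status is unaffected. The flare rule has the fault only when TP1 crosses New Year, about half of first-dose dates if these are spread evenly.

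The fault is certain for any such record, provided the imputed date is carried into the period tables. The text gives no alternative, but does not say so expressly for year-only dates. The effect on results cannot be sized because the number of year-only dates is not in the documents. It is probably small. The calendar shares rest on even first-dose and onset dates and on full 12-month treatment.

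**What to change.** - **8.2.1.1:** when day and month are missing and the year is accepted, impute the later of first study drug intake and 1 January of the recorded year. Keep the AE treatment-emergent. Assign TP1 or TP2 from the imputed date, and neither if it falls after EOT.
- **7.4.5.1:** apply the same later-of rule to years within the existing interval. Leave other years missing, as now.
- **8.2.1:** reconcile the sentence on events from 121 days after EOT with the EOT + 180 days limit, so that an imputed 1 January date is classified in one way.

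The cost is one sentence in each of three places and a small programming change, with no new data. The change does not resolve every case. Dates in the first-dose year, and in any year that overlaps TP1, remain ambiguous and still default to TP1. The gain is that an imputed onset never contradicts the recorded year.
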